5.2 Methods for Continuous Secondary Endpoint

5.2.1 Descriptive Statistics

CSF NAD (or other metabolites of the NAD metabolome) measured by LC-MS will be summarized by group for visits V1 and V4 using descriptive statistics (N, mean, standard deviation). Descriptive statistics will be based on non-imputed data. Data will be presented both in tabular and graphical format.

5.2.2 Primary Inferential Analysis

Analysis of covariance (ANCOVA) between the dose escalation (DE-group) and the dose stable group group (DS-group), i.e. the regression of CSF NAD (or other metabolites of the NAD metabolome) at week 12 depending on randomization group and adjusted for CSF NAD (or other metabolites of the NAD metabolome) at baseline. No additional adjustments/covariates will be used. No correction for multiple testing will be performed.

The formula for this calculation in R is:

```
NAD_at_V4 ~ Group + NAD_at_V1
```

5.2.3 Effect Estimates

The primary effect estimate will be the B-coefficient with confidence intervals and Cohen's d. Cohen's d will be calculated as the difference in the means between two groups and divided by the pooled standard deviation.

The Beta coefficient will be calculated in R in the following manner:

```
Beta_coefficient = summary(lm_object)$coefficients
```

Confidence intervals will be calculated in R in the following manner:

```
Confidence_intervals = confint(lm_object)
```

P-values will be retrieved from the summary of the lm_object:

```
P_values = summary(lm_object)$coefficients
```

5.2.4 Assumption Checks and Alternative Analyses

Assumptions for ANCOVA will be tested in the following manner:

Normal distribution of residuals: Normality of residuals will be assessed by QQ-plots and the Shapiro-Wilk test.

5.2.5 Missing Data

For the primary outcome, missing data occur if a patient has not completed the study or CSF collection has not been successful within the time window of the final visit 12 weeks \pm 7 days.

As the primary analysis uses two timepoints (V1 and V4), in the case of a participant missing V4 measurements, this patient will not be included in the analysis.

5.2.6 Sensitivity Analyses

Sensitivity analysis will be performed by comparing the results of analysis with the FAS and PPS populations. If there is a notable difference this will be commented upon.

5.2.7 Secondary Analyses of the Secondary Endpoint

The *secondary analysis* of the *secondary endpoint* will be:

- Analysis of covariance (ANCOVA) between the dose stable (DS-group) and the placebo group group (PL-group), i.e. the regression of CSF NAD (or other metabolites of the NAD metabolome) at week 12 depending on randomization group and adjusted for CSF NAD (or other metabolites of the NAD metabolome) at baseline. No additional adjustments/covariates will be used. No correction for multiple testing will be performed.

The above mentioned analysis will be performed in the same manner as the primary analysis for the secondary outcome (see section 5.2.2).

5.3 Methods for Continuous Exploratory Endpoints

As described in section 4.4, due to the nature of the exploratory outcomes, the analysis method is subject to change. The preliminary plan is that they will be analysed in the same manner as the primary endpoint if they have observations at V1, V2, V3 and V4 (see sections 5.1.2 and 5.1.7) and the same manner as the secondary endpoint if they only have observations at V1 and V4 (see sections 5.2.2 and 5.2.7).

5.4 Additional Explorative Analyses

5.4.1 Correlation analyses

Explorative correlation analyses comparing the following correlations with either Spearman or Pearson correlations are planned:

- Change in cerebral NAD levels measured by ^{31}P -MRS vs NAD levels in CSF.

- Change in cerebral NAD levels measured by ^{31}P -MRS vs NRRP expression.
- Change in cerebral NAD levels measured by ^{31}P -MRS vs ADRP expression.
- Change in NAD levels in CSF vs NRRP expression.
- Change in NAD levels in CSF vs ADRP expression.
- Change in cerebral NAD levels measured by ^{31}P -MRS vs the following clinical rating scales:
 - ADAS-Cog 13
 - CDR-SB
 - MoCA
- Change in NAD levels in CSF vs the following clinical rating scales:
 - ADAS-Cog 13
 - CDR-SB
 - MoCA
- Change in NRRP expression vs the following clinical rating scales:
 - ADAS-Cog 13
 - CDR-SB
 - MoCA
- Change in ADRP expression vs the following clinical rating scales:
 - ADAS-Cog 13
 - CDR-SB
 - MoCA
 -
- Change in Blood NAD levels vs NAD levels in CSF
- Change in Blood NAD levels vs cerebral NAD levels measured by ^{31}P -MRS
- Change in Blood NAD levels vs NRRP expression
- Change in Blood NAD levels vs ADRP expression

5.5 Sample size

Our primary null hypothesis (H_0) is that the NR-induced increases in cerebral NAD levels (measured by ^{31}P -MRS), or NRRP expression (measured by FDG-PET) are not dose-responsive. The alternative hypothesis (H_A) is that at least one of these measures will be dose responsive. In the NADPARK study, all three measures showed a highly significant increase in the group receiving 1000 mg NR ($n = 15$) compared to the placebo group ($n = 15$). In the NADPARK study⁹, treatment with 1000mg of NR led to an increase in cerebral NAD-levels by a factor of 1.27 from baseline in the treatment group, whereas the change in the placebo group was negligible at -0.43%. Under the H_A , we assume that cerebral NAD levels will increase in a linear fashion in the 2000 mg NR and 3000 mg NR groups, respectively. Based on these assumptions and given a type I error rate of 5% ($\alpha = 0.05$) and a type II error rate of 10% ($\beta = 0.1$, power = 90%), we estimated that a sample size of 30 individuals will be required in the dose escalation group. Accounting for drop-out and statistical safety margin, we estimate that the study requires 40 subjects in this group.

For the secondary outcomes, we assume that the metabolomic analyses will have sufficient power, since they produced very large effect sizes and highly significant results in the NADPARK study with 15 individuals per group.

6 Safety Analyses

General safety evaluations will be based on the incidence, intensity, and type of AEs, and clinically significant changes in the patient's physical examination findings, vital signs, and clinical laboratory results. Only AE grade 2 and above will be recorded. Safety variables will be tabulated and presented for all patients in the safety set.

6.1 Adverse Events

6.1.1 Descriptive Statistics

The frequency and severity of adverse events (AE) will be presented in tabular format between all three randomization groups and NR dose levels (1000 mg, 2000 mg and 3000 mg). AEs are evaluated as being either unrelated, unlikely, possible, probable or definite in relation to the investigational medicinal product (IMP). AEs will be grouped by status; Moderate or Severe and grouped by relation to the IMP. AEs will be presented by number and by percentage of group. The safety analysis set (SAS) will be used for analysis. The variables are continuous. No further statistical testing will be performed on the AEs. We refer the reader to the study protocol for a more detailed definition of AE severity and registration procedures.

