3.4 Adherence and Protocol Deviations

3.4.1 Adherence to Allocated Treatment

Compliance is assessed based on the percentage of subjects who have taken the scheduled number of pills. It is defined as:

% compliance = (number of capsules taken / number of capsules supposed to have been taken) x 100%.

The number of capsules supposed to have been taken will be calculated as the duration of treatment (end of study medication – start of study medication) multiplied by 12 per dispensation of study medication. In this study 6 capsules are taken in the morning and 6 capsules in the evening.

The mean \pm SD of study drug compliance over the whole study period and between individual visits will be presented in a table by treatment group.

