3.5 Analysis Populations

The Full Analysis Set (FAS) will be performed using the intention to treat population, defined as all patients randomly assigned to a treatment group and attended the baseline visit.

The Safety Analysis Set will include all patients having received at least one dose of study treatment after randomisation.

The Per Protocol Analysis Set (PPS) will include all randomised patients meeting the study eligibility criteria and with no major protocol deviations affecting the treatment efficacy.

4 Endpoint Definitions

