4.5 Overview of Endpoints

Endpoint level	Analysis level	Endpoint	Timeframe	Type
Primary Endpoint				
	Primary	Cerebral NAD ³¹ P-MRS: Difference between DE-group and DS-group.	84 ± 7 Days	Continuous
	Secondary	Cerebral NAD ³¹ P-MRS: Difference between DE-group-, DS-group, and PL-group.	84 ± 7 Days	Continuous
	Secondary	Cerebral NAD ³¹ P-MRS: Difference between DS-group and PL-group.	84 ± 7 Days	Continuous
Secondary Endpoint				
	Secondary	NAD levels in CSF: Difference between DE-group and DS-group.	84 ± 7 Days	Continuous
	Secondary	NAD levels in CSF: Difference between DS-group and PL-group.	84 ± 7 Days	Continuous
Exploratory Endpoints (see section 4.4)				
Safety				
	N/A	Number and severity of adverse events between treatment groups and study visits.	During trial	Continuous

5 Analysis Methods

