6.2 Clinical Laboratory Parameters

Safety clinical laboratory parameters were collected and assessed, both to be used to identify adverse events and for exploratory analyses. Clinical laboratory parameters will be summarised by treatment group and visit.

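### SAP 6.1.1 plans AE percentages by NR dose level with no number at risk, exposure or dose-assignment rule, although planned exposure per patient is 12 weeks in the dose-stable and placebo cells and 4 weeks at each escalation dose

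*SAP*

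**What the plan says.** SAP 6.1.1 says that the frequency and severity of AEs "will be presented in tabular format between all three randomization groups and NR dose levels (1000 mg, 2000 mg and 3000 mg". It adds that "AEs will be presented by number and by percentage of group" and that "The safety analysis set (SAS) will be used for analysis". SAP 3.5 defines that set per patient, not per dose: "The Safety Analysis Set will include all patients having received at least one dose of study treatment after randomisation". No testing of AEs is planned.

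The safety objective in protocol section 2 concerns tolerability at 1000, 2000 and 3000 mg per day, and its endpoint spans treatment groups and dose levels. SAP 4.5 words the same endpoint differently: "Number and severity of adverse events between treatment groups and study visits". For laboratory values, SAP 6.2 says "Clinical laboratory parameters will be summarised by treatment group and visit", and SAP 6.3 treats vital signs in the same way.

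The schedule is given in protocol section 2 and SAP 1.2. DS receives 1000 mg for 12 weeks, placebo runs for 12 weeks, and DE receives 1000, 2000 and 3000 mg for 4 weeks each. Protocol 8.2 records AEs from after baseline until 7 days after the last visit. Protocol 8.3 records the onset date of each event. Protocol 6.4.1 provides no follow-up for withdrawn patients.

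**The concern.** A dose level is not a randomised group, because each DE patient passes through all three doses. A percentage of group therefore has no defined denominator at a dose level. SAP 6.1.1 leaves open:

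- whether DS and DE are combined at 1000 mg;
- whether an AE belongs to the dose at onset or to every dose during which it continues;
- where the 7 days after the last visit belong;
- whether DE patients who left before a dose step still count in the denominator for that step.

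The dose-level table is the one readers will use to judge tolerability by dose. A cell that covers 12 weeks collects more AEs per patient than a cell that covers 4, whatever the dose does. The choices left open can therefore produce an apparent dose pattern when the risk is the same throughout.

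**Working it through.** The documents give no AE rate, so there is no planned figure to reproduce. The hazards below are assumptions, constant over time and equal at all doses unless stated otherwise.

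**Inputs.** Placebo 20, DS 20 and DE 40 patients (protocol 4.2). Exposure is 12 weeks in one cell for DS and placebo, and 4 weeks per dose for DE. Assumed hazards are 0.02, 0.05 and 0.10 per person-week. Formula: P(w) = 1 − exp(−hazard × w).

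**1. Planned person-weeks.** DS 20 × 12 = 240; placebo 240; DE 40 × 4 = 160 at each dose. DS and DE combined at 1000 mg: 240 + 160 = 400, against 160 at 3000 mg, a ratio of 2.5. If the 7-day tail is attributed to the last dose, DS has 20 × 13 = 260 and DE at 3000 mg has 40 × 5 = 200, so the ratio is 420:200 = 2.1. Protocol 3.1 speaks of 30-day periods; this leaves the 3:1 ratio per patient unchanged.

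**2. Patients with an AE, assigned to the dose at onset, no drop-out.** The combined 1000 mg percentage is (20 × P(DS weeks) + 40 × P(4)) / 60.

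| Hazard | DS or placebo, P(12) | DE 3000 mg, P(4) | Ratio | Combined 1000 mg | Ratio to 3000 mg |
|---|---|---|---|---|---|
| 0.02 | 21.3% | 7.7% | 2.78 | 12.2% | 1.59 |
| 0.05 | 45.1% | 18.1% | 2.49 | 27.1% | 1.50 |
| 0.10 | 69.9% | 33.0% | 2.12 | 45.3% | 1.37 |

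With the tail attributed to the last dose, DS and placebo have 13 weeks and DE 3000 mg has 5. The ratios become 2.41, 2.16 and 1.85 with the groups kept apart, and 1.34, 1.27 and 1.17 with DS and DE combined at 1000 mg.

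**3. A different assignment rule.** Suppose an AE also counts at every later dose during which it continues. In the extreme case where no event resolves, at 0.05 and without the tail, DE shows P(4) = 18.1%, P(8) = 33.0% and P(12) = 45.1% at 1000, 2000 and 3000 mg. DE 3000 mg then equals DS (45.1%) and exceeds the combined 1000 mg figure, which stays at 27.1% because no DE patient is at 1000 mg after week 4. The direction depends on the missing rule.

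**4. DE only.** Planned exposure is equal (4 weeks per dose) only if the tail is excluded. With the tail, 3000 mg has 5 weeks against 4, and P(5)/P(4) is 1.24, 1.22 and 1.19 at the three hazards, against the highest dose. Dose is also tied to time on study. With an assumed hazard of 0.10 in weeks 0–4 and 0.05 later in every arm, and no dose effect, DE alone shows 33.0% at 1000 mg and 18.1% at 2000 and 3000 mg.

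**5. Drop-out.** Suppose the safety-set size of 40 is the denominator and n DE patients reach the 3000 mg step. At 0.05 the expected percentage is 18.1% × n/40: 16.3% for n = 36, 15.4% for n = 34 and 13.6% for n = 30. With number at risk it stays at 18.1%. The documents give no drop-out figure. The lowest n is the 30 required in SAP 5.5, whose margin to 40 is explained as follows: "Accounting for drop-out and statistical safety margin, we estimate that the study requires 40 subjects in this group". A loss of ten is therefore an assumed upper value.

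**The case against.** Several points on the other side are sound. SAP 4.5 already names AEs by group and study visit. DE dose steps are supplied at visits (protocol 6.1, specification 10), so that breakdown is a dose-period table with concurrent DS and placebo columns, and carrying it out would remove most of the problem. However, 4.5 is one line in an overview table, gives no number at risk, and is not what 6.1.1 specifies.

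A reader might infer that the plan favours 2000 and 3000 mg under any reading. The documents do not support that: the direction in step 2 needs a dose-at-onset rule that the SAP does not state, and step 3 shows it can differ under another rule. Nor is 2.78 the only figure for the lowest hazard, since the tail brings it down to 2.41.

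The drop-out effect is also conditional. SAP 3.3 provides for patients who finish assessments without finishing the intervention, so stopping treatment need not end observation.

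The comparison of safety set and per-protocol set in SAP 6.1.2 does not settle the matter. The per-protocol set leaves out patients who discontinued early, and it keeps the 12-week against 4-week imbalance.

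**Conclusion.** The point holds as a gap in SAP 6.1.1. The planned dose-level table lacks a number at risk, exposure and an assignment rule, and its cells differ threefold in planned weeks per patient. That threefold difference comes from the schedule without the tail and needs no AE rate.

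If AEs are assigned to the dose at onset, then at equal risk the DS or placebo percentage is 2.78 to 2.12 times that at DE 3000 mg, or 2.41 to 1.85 times with the 7-day tail. With DS and DE combined at 1000 mg the ratio is 1.59 to 1.37, or 1.34 to 1.17 with the tail. These ratios rest on assumed constant hazards of 0.02 to 0.10 per person-week and no drop-out. Any dilution of the 3000 mg percentage by drop-out depends on a figure that the documents do not give.

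Severity is minor. The AE analysis is descriptive and no decision rule uses it. A reader might conclude that the trial's safety comparison as a whole is unsound; it is not, because the three arms have equal planned duration and the 12-week table by arm is unaffected by this point.

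**What to change.** In SAP 6.1.1:

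1. Assign each AE to the dose at onset, and list onsets in the 7 days after the last visit on a separate line.
2. Keep DS and DE separate at 1000 mg.
3. Make the dose-safety table one of AEs by visit interval (V1–V2, V2–V3, V3–V4) for DE, DS and placebo side by side, in line with SAP 4.5.
4. In each cell show patients on treatment at the start of the interval, person-weeks, patients with an AE and number of AEs. Use the number at risk as the denominator for percentages.
5. Keep the 12-week table by arm on the safety analysis set.

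Person-week rates should not be combined across intervals. In the example of step 4, with no dose effect, 1000 mg would show (16 DS + 16 DE events)/400 = 0.080 against 0.050 at 2000 and 3000 mg. The interval table shows 18.1% in all three arms in weeks 5–8.

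The cost is one or two extra descriptive tables from data already collected: onset dates, visit dates, and treatment duration, which SAP 3.4.1 already takes for compliance ("multiplied by 12 per dispensation of study medication"). Cells are small: at most 40 DE, 20 DS and 20 placebo patients, or 160, 80 and 80 person-weeks per interval. At 0.05 per person-week, the exact 95% interval is 0.022 to 0.099 for 8 events in 160 person-weeks (DE) and 0.014 to 0.128 for 4 in 80 (DS). The table also does not remove the selection of patients who tolerated earlier steps.

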6.1.2 Sensitivity Analyses

Sensitivity analysis of data will be performed by comparing the results of analysis with the SAS and PPS populations. If there is a notable difference this will be commented upon.

6.2 Clinical Laboratory Parameters

Safety clinical laboratory parameters were collected and assessed, both to be used to identify adverse events and for exploratory analyses. Clinical laboratory parameters will be summarised by treatment group and visit.

6.3 Vital Signs

Changes in vital signs (including systolic and diastolic blood pressure (mmHg), heart rate (beats per minute) and weight (kg)) will be summarised by treatment group and visit.

7 Statistical Software

All statistical analyses will be done in R 4.4.1 (R Foundation for Statistical Computing, Vienna, Austria).

8 References

8.2 Reference to Data Handling Plan

Data handling and management is outlined in the trial protocol: N-DOSE AD protocol V4.0.

8.3 Reference to the Trial Master File and Statistical Documentation

Data handling and management is outlined in the trial protocol: N-DOSE AD protocol V4.0.

8.4 Reference to other Standard Operating Procedures or Documents

The trial protocol: N-DOSE AD protocol V4.0, was adhered to and followed when writing the SAP.
